#### 1.4 SUMMARY OF KNOWN POTENTIAL RISKS WITH STUDY MEDICATION

Pruritus has been observed in the multiple dose trials of OCA in primary biliary cirrhosis (PBC) and was the most common AE seen in the PBC 747-202 Trial, DB phase, with 67% of patients reporting a treatment emergent AE (TEAE) of pruritus. There was a relationship between the dose of OCA administered and the incidence (at 25 mg and 50 mg only), severity, and the timing of the onset of pruritus, which occurred almost invariably within the first 14 days of treatment at 50 mg. Pruritus was least tolerated at 50 mg with 24% of patients discontinuing at this dose due to pruritus.

In the 747-201 Trial, DB phase, pruritus was the most common AE that occurred in any treatment group, 50 mg (94%) and 10 mg (70%), and at a rate higher than in the placebo (30%) group. Similarly, pruritus has been the most commonly reported AE in the 747-201 LTSE to date. The severity of pruritus shows an apparent improvement with increasing dose of OCA in the LTSE. This suggests that patients who do not develop severe pruritus at lower doses are likely to tolerate higher doses if titrated up.

The mechanism of pruritus in cholestatic liver disease is unknown. Recently, autotaxins and lysophosphatidic acid have been implicated in pruritus of cholestasis [Kremer 2009, 2010, 2011]. Recent data [Kremer 2011] suggest that autotaxins may be increased in patients with the worst pruritus taking 50 mg in the 747-202 trial and that patients with high autotaxin levels were more likely to develop severe pruritus. However, plasma autotaxin levels did not explain the pruritus in the majority of patients. Assays of the plasma from the subjects receiving 250 mg dose in the multiple dose normal volunteers trial (747-102) did not show a difference in autotaxin levels between the pruritic and non-pruritic subjects. Bile acid concentrations in the PBC trial 747-202 have not shown an association with pruritus.

In the PBC 747-202 Trial, DB phase, besides pruritus, only nausea (mild or moderate) was seen more frequently in all 3 OCA groups than in the placebo group. In the 747-201 DB phase, only urinary tract infection was seen more frequently in both OCA groups than the placebo group. The current IB outlines other AEs observed in association with the use of OCA.

## 2. TRIAL OBJECTIVES

### Primary

- Change in MELD score at 6 weeks
- Incidence of serious adverse events (SAEs) during the treatment phase

### Secondary

- Any SAEs during the follow-up phase
- SAEs attributable to the study medicine during the treatment and follow-up

phases

- AEs and discontinuation rates during the treatment and follow-up phases
- Change in MELD score at 90 and 180 days
- Change in Child-Pugh score at 6 weeks and at 90 and 180 days
- Mortality rate at Week 6 and at 90 and 180 days
- Rates of hospitalization and lengths of stay
- Changes in intestinal inflammation and bacterial translocation
- Changes in serum oxidative stress, cytokines, and activation of innate immunity.

### **3. INVESTIGATIONAL PLAN**

#### **3.1 OVERALL TRIAL DESIGN AND PLAN**

##### **Design**

This is a phase 2, double-blind, placebo-controlled trial of OCA in patients with moderately severe AH. In the DB phase, approximately 60 patients (30 patients per arm) will be randomized in a 1:1 ratio to 1 of 2 treatment arms: (a) placebo, or (b) 10 mg OCA. Study medication will be administered orally, once daily for 6 weeks.

#### **3.2 SCHEDULE OF TRIAL PROCEDURES**

The Schedule of Trial Procedures is provided in Table 1.

Table 1: Schedule of Trial Procedures

	Screening	Treatment Phase 				Follow-up phase		
		D0	D14	D28	D42	D90	D120	D180
Informed consent	X							
Confirmation of eligibility criteria	X	X						
Randomization		X						
History and physical	X	X	X	X	X	X	X	X
Assess Liver Scores: MELD, Child Pugh and/or Discriminant Function	X	X	X	X	X	X	X	X
AUDIT and NIAAA Questionnaires	X							
Timeline Followback Questionnaire	X	X	X	X	X	X	X	X
Concomitant medicines	X	X	X	X	X	X	X	X
Adverse events		X	X	X	X	X	X	X
Electrocardiogram	X				X			
Evaluation of compliance			X	X	X			
Dispense study medication 		X	X	X	X			
CBC, CMP, INR	X	X	X	X	X	X	X	X
Pregnancy test 	X	X	X	X	X			
Special investigations 		X			X			
Specimen Banking 		X	X	X	X	X	X	X

 There is a telephone visit on D7 and D21.  Bottle(s) will be dispensed to the subjects for at-home dosing at the D0 and D14 visits. Subjects will be instructed to dose at the clinic at the D14, D28 and D42 visits.

 A serum pregnancy test (in women of childbearing potential) will be done at Screening. Urine pregnancy tests will otherwise be conducted.

 **Special investigations** for this protocol consist of serum FGF19, bile acid C4, OCA and conjugates, fasting free fatty acids, lipid profile, insulin, adiponectin, measures of bacterial translocation (plasma LPS and sCD14), cytokine measurements (serum TNF- $\alpha$ , IL-1, IL-6, and IL-8), markers of oxidative stress, apoptosis, and stool for calprotectin.

 Specimens to be banked include genomic DNA at D0, blood mononuclear cells at D0, D28 and D42 and blood ( serum and plasma) samples at D0, D14, D28, D42, D90, D120 and D180. Stool samples collected at D0 and D42 will also be banked for future ancillary studies.

### 3.2.1. Duration of Trial by Phase

Time expected for all patients to be enrolled:	~ 15 months
Duration of individual patient participation:	42 days (6 weeks) during the treatment phase 5 months during the follow up phase
Total duration of trial (excluding data collection and analysis):	21 months

The end of this trial will occur when the last patient(s) completes the D180 visit.

## 4. PATIENT SELECTION

### 4.1 PATIENT POPULATION

This trial will be conducted at 3 sites with experience in treating patients with AH. Prospective patients will be identified primarily from the hospital and/or outpatient clinics, or may be referred by physicians from other hospitals.

Throughout this protocol, the terms 'Principal Investigator (PI)', 'investigator' and 'investigator or designee' is used synonymously. Irrespective of the term used, the intention remains the same: that the overall trial responsibility remains with the PI who has agreed to personally conduct or supervise the trial and who may delegate aspects of the trial conduct, to appropriate, qualified trial site staff who have been informed about their obligations in meeting the above commitments.

Patients will be selected according to the following criteria.

### 4.2 INCLUSION CRITERIA

If used, the term 'baseline' (BL) within this protocol, unless otherwise specified, is intended to mean, 'prestudy' or 'pretreatment' (of study medication). It refers to values obtained during the Screening or Day 0 visits, prior to the patient's first dose of study medication.

Patients must meet all of the following criteria to enter the trial.

**(a)** Individuals  $\geq 21$  years with a diagnosis of acute AH. The diagnosis of acute alcoholic hepatitis will be based on clinical features and testing including hepatomegaly, jaundice, fever, leukocytosis, compatible liver biochemistries in the context of heavy alcohol consumption. A liver biopsy is not mandatory, but will be required to confirm the diagnosis if a firm diagnosis of AH cannot be made on clinical and laboratory criteria

**(b)** Moderate severity defined as MELD score > 11 and < 20

**(c)** Heavy alcohol consumption (defined as > 40 grams per day on average in women and > 60 grams per day on average in men for a minimum of 6 months and within the 6 weeks prior to study enrollment)

**(d)** Written informed consent

**(e)** Negative urine pregnancy test where appropriate

**(f)** Women of child bearing potential should be willing to practice contraception throughout the treatment period

### **4.3 EXCLUSION CRITERIA**

**(a)** Significant active infection (e.g. sepsis or SBP). Subjects can be reconsidered after the infection is under control.

**(b)** Serum creatinine > 2.5 mg/dL

**(c)** Must not have received systemic steroids for a duration of > 1 week during the screening period or on the day of randomization and must not be receiving any experimental medicines for AH

**(d)** Presence of any other disease or condition that is interfering with the absorption, distribution, metabolism, or excretion of drugs including bile salt metabolism in the intestine. Patients who have undergone gastric bypass procedures will be excluded (gastric lap band is acceptable).

**(e)** Participation in another investigational drug, biologic, or medical device trial within 30 days prior to screening

### **4.3 PATIENT WITHDRAWAL FROM THE TRIAL**

#### **4.3.1 Reasons for Mandatory Trial Discontinuation**

If a female patient becomes pregnant, she must stop taking study medication and must be withdrawn from the trial. The patient must be followed by the investigator through the end of her pregnancy. The mother (and infant) will be followed as considered appropriate by the investigator and the study designated physician ([name] or his designee). For reporting purposes, pregnancy is not considered a serious adverse event (SAE).

During the trial, if Maddrey's Discriminant Factor (DF) increases by 5 points and also exceeds 32, or MELD scores increases by 5 points and also exceeds 20, the study

medication should be stopped, however the participant will remain in the trial, completing procedures as detailed in the Schedule of Procedures (Table 1). Treating physicians may offer any other treatment that is considered as medically indicated and appropriate.

#### **4.3.2 Other Reasons for Trial or Treatment Discontinuation**

The following events are considered appropriate reasons for a patient to discontinue from the trial:

- The patient withdraws consent or requests to be withdrawn from the trial. It is fully understood that all patients volunteer for the trial and that they may withdraw their consent at any time.
- The patient experiences an adverse event that in the opinion of the site investigator or the primary investigator of the trial (i.e., study designated physician, [name]) is caused by or exacerbated by any of the trial procedures or study medication, of sufficient intensity to warrant discontinuation.
- The patient refuses to comply with the requirements for trial participation.

When possible, the investigator should discuss the potential discontinuation of a patient with the study designated physician ([name] or his designee) in advance.

#### **4.3.3 Patient Discontinuation Notification**

The investigator must notify the study designated physician ([name] or his designee) as soon as possible if any patient prematurely discontinues from the trial. The date when the patient is withdrawn and the primary reason for discontinuation must be recorded in the CRF; additional information may be requested to complete a discontinuation narrative. Patients will be considered “lost to follow up” only after reasonable, documented attempts to reach the patient prove unsuccessful. In all cases, a reasonable effort must be made to determine the reason(s) that a patient fails to return for required trial visits or discontinues from the trial.

If a subject stays in the study but discontinues study medication (either by participant’s choice, or by the investigator’s decision), then study measurements should be performed according to the Schedule of Trial Procedures, Table 1, (rather than expediting study visits, or measurements).

## **5. INVESTIGATIONAL PRODUCT (IP)**

### **5.1 DESCRIPTION OF IP**

For the purpose of this protocol, the term ‘investigational product (IP)’ is interchangeable with the term ‘study medication’.

### **5.1.1 Study Medication**

Intercept Pharmaceuticals will provide study medication (OCA and matching placebo) which are white or light blue-green round tablets engraved with 'INT' on one side and '3547' on the other side. All study medication will be provided as a tablet for oral administration. The tablets are packaged in high density polyethylene (HDPE) bottles with 30 tablets per bottle and closed with an induction seal and child proof cap. Bottles will also include two desiccant packets and cotton coil.

All study medication (OCA and matching placebo) will be manufactured according to Good Manufacturing Practice (GMP).

### **5.1.2 Treatment Phase**

Study medication will be provided to each site (pharmacy) as open label product, overlabeled at each site and blinded based on the randomization scheduled, and then provided to subjects in a blinded manner (i.e., the investigator, site staff and patient will be unable to distinguish treatment assignment). Study medication will consist of either 10 mg OCA or matching placebo tablets.

## **5.2 PACKAGING, LABELING, AND STORAGE**

The packaging and labeling of study medication for provision to the clinical trial sites will be performed according to GMP standards by designated qualified vendors.

The designated IP distribution vendor will be responsible for the distribution of the study medication to the clinical trial sites. Study medication should be stored at controlled room temperature (15°C to 30°C) and protected from excess humidity.

Study medication will be packaged for the trial as described below.

### **5.2.1 Packaging and Labeling**

Study medication for the trial will be packaged and labeled as open label bottles containing 30 tablets and sent to each investigative site (pharmacy). Each site will be responsible for overlabeled (i.e., blinding) the bottles with a unique non sequential bottle number for the purpose of identifying and allocating the bottle. The bottle number will not reveal any information about the treatment dose contained in the bottle. The investigative pharmacist at each individual trial site will prepare the study medication for appropriate dispensing to the subjects according to standard operating procedures.

## **5.3 DOSE, ADMINISTRATION AND BLINDING**

Two (2) treatment groups will be evaluated in the trial: (a) placebo or (b) 10 mg OCA. Study medication will be administered orally, once daily for 6 weeks (42 days) during the study. Each daily dose will be made up of 1 tablet.

Patients will be instructed to begin dosing on the day after the Day 0 visit (i.e., on Day 1) and to take study medication with water, approximately 30 minutes prior to breakfast. Patients must be instructed to swallow the tablet whole; they must not chew, divide, or crush the tablet.

### **5.3.1 Dispensing Procedures**

On Day 0, after confirmation of patient eligibility and randomization, the investigator or designee will dispense 1 bottle of study medication to the patient. Before leaving the clinic/hospital, the study staff will ensure that the patient fully understands the dosing instructions. Additional study medication (i.e., a second bottle) will be dispensed on Day 14. The clinical trial site investigator may adjust the number of bottles (1 or 2) dispensed to the subject based on clinical judgment and visit scheduling to ensure an adequate supply of study medication is available for dosing between clinic visits.

### **5.3.2 Blinding**

All study medication will be visually identical for the OCA and placebo treatment arms, thus ensuring the double-blind nature of the trial. Study medication bottles will not be labeled with either a patient randomization number or tablet strength, to ensure that neither patient nor investigator is unblinded.

### **5.3.3 Missed Doses**

Patients who miss a dose of study medication should be instructed to take it later the same day, as soon as they remember. 'Missed' doses should not be taken on a subsequent day (i.e., the patient should not take more than the prescribed daily dose).

### **5.3.4 Overdosage**

The maximum dose of OCA that has been given to humans is 500 mg as a single dose and 250 mg as a multiple dose. Reversible increases in aminotransferases were seen in most of the healthy volunteers who took 250 mg OCA. There is no specific information available regarding the treatment of possible overdose with OCA. If overdose occurs in a patient enrolled in the trial, general medical supportive measures should be provided, including observation and follow up (e.g., serum chemistry) as appropriate. Due to the extensive enterohepatic recirculation of the drug it is likely that it will take several days before blood (and organ) concentrations of the drug will decrease. Treatment with cholestyramine (Questran™), colestevlam (Welcol™) and other bile acid sequestrants is both logical and recommended given that they should bind and eliminate the drug in feces. Although there is no experience with OCA, plasmapheresis might be expected to reduce circulating levels of the drug. The study designated physician ([name]) should be notified immediately in the event of a significant overdose.

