#### **5.6 PRIOR AND CONCOMITANT MEDICATIONS OR PROCEDURES**

Relevant information about all concomitant drugs (including prescribed, over the counter, or herbal preparations) taken prior to and during the trial must be recorded in the source documents and CRF, as well as any dose or dose regimen changes that occur during the trial.

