#### **5.7 TREATMENT COMPLIANCE**

The investigator should assess the patient's compliance with dosing of study medication on an ongoing basis, at least at each visit, and confirm by conducting drug accountability (i.e., count of returned tablets).

Patients should be instructed to retain all bottles of study medication, even if empty, and to return them to the investigator at the subsequent visit. The investigator or designee should perform drug accountability and, if applicable, follow up with the patient to retrieve any study medication that has not been returned.

If the investigator has concerns about a patient's dosing compliance s/he should discuss this with the patient, assess the reasons for noncompliance and the likelihood that the patient will remain noncompliant, and notify the designated study physician accordingly. Continued trial eligibility should be assessed based on the patient's compliance with study medication dosing and clinic visits.

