### **6.2.3 D7 Procedures ( $\pm$ 1 days)**

- This consists of a telephone visit where the participant will be inquired about his/her well-being, compliance with IP, concomitant medications and alcohol use.
- The subject should be reminded that fasting (8 hours) is required prior to his/her next visit. The subject should not take study medication on the morning of the next clinic visit (D14) as s/he will dose at the clinic.

Ascertain that participant is not receiving concomitant systemic corticosteroids

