**6.2.7. Day 42 Procedures (+ 2 days) - Must present after at least 8 hours of fasting**

- Perform a physical examination
- Record vital signs
- Assess Liver Scores: MELD, Child Pugh and Discriminant Function
- Alcohol consumption history — Timeline Followback Questionnaire
- Assess and record AEs
- Review and record concomitant medications. Confirm that participant is not receiving concomitant systemic corticosteroids.
- Assess study medication compliance and perform accountability and obtain any remaining study medication from patient
- Obtain blood samples for serum chemistry, hematology and coagulation tests
- Perform a urine pregnancy test in females of childbearing potential
- Perform a standard 12-lead electrocardiogram (ECG)
- Obtain blood samples for special investigations as outlined in section 3.2
- Instruct the patient to take the final dose of study medication, at the clinic, with water and approximately 30 minutes prior to eating
- Perform biosample (blood and stool) banking for future use

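### The protocol expects bile acid sequestrants to remove OCA, but no rule avoids or spaces them while patients take study drug

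*Combined protocol and SAP*

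**What the plan says.** Section 5.3.4 (Overdosage) recommends sequestrants after an overdose because they are expected to take OCA out of the body: "other bile acid sequestrants is both logical and recommended given that they should bind and eliminate the drug in feces". The same section notes that "There is no specific information available regarding the treatment of possible overdose with OCA", and it describes extensive enterohepatic recirculation of the drug.

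The places where a rule for ordinary use could sit say this:

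- **Exclusion (c), section 4.3:** limits systemic steroids and experimental medicines for alcoholic hepatitis. No other class of medicine is named.
- **Exclusion (d), section 4.3:** "Presence of any other disease or condition that is interfering with the absorption, distribution, metabolism, or excretion of drugs including bile salt metabolism", the last referring to the gut. Its worked example is gastric bypass.
- **Dosing, section 5.3:** patients are told "to take study medication with water, approximately 30 minutes prior to breakfast" and to swallow the tablet whole. No gap from other medicines is given.
- **Concomitant medication, section 5.6:** "Relevant information about all concomitant drugs (including prescribed, over the counter, or herbal preparations) taken prior to and during the trial must be recorded".
- **Contacts during treatment, section 6.2:** the telephone visits ask about "compliance with IP, concomitant medications and alcohol use". The clinic visits carry an instruction such as "Review and record concomitant medications. Confirm that participant is not receiving concomitant systemic corticosteroids". Corticosteroids are the only class singled out.
- **Compliance, section 5.7:** the investigator assesses dosing and is to "confirm by conducting drug accountability (i.e., count of returned tablets").

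The abbreviation list defines BAS as bile acid sequestrants, but the abbreviation is not used again.

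**The concern.** The protocol names a class of medicines that it expects to bind the study drug and carry it out in the feces. It then lets patients take that class during the 42 dosing days with no instruction to avoid, stop or space it. A site that follows the plan exactly could give both together.

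Placebo patients have no OCA to lose, so any lost exposure falls on one arm only. It would shrink the MELD difference toward zero, and an intention-to-treat analysis of observed values cannot put it back. Table 1 schedules the special investigations, including C4, FGF19 and OCA with its conjugates, at Day 0 and Day 42 only. A patient on a sequestrant at Day 42 would therefore have that patient's only scheduled on-treatment values affected.

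**Working it through.** **1. Is there a rule anywhere?** Set side by side, the sections above give three kinds of control.

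| Control | Where | Does it reach sequestrants? |
|---|---|---|
| Eligibility | 4.3 (c), (d) | No. (c) names steroids and experimental medicines; (d) covers a disease or condition, not a medicine |
| Dosing instructions | 5.3, 6.2.2 to 6.2.7 | No. Water, timing before breakfast and swallowing whole only |
| Recording and review | 5.6; D0, D7, D14, D21, D28, D42 | Use would probably be seen, but no action is specified |

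The tablet count in 5.7 measures tablets taken, not drug absorbed, so it cannot detect binding.

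**2. Reproduce the plan's figure.** Section 10.2 gives 30 per arm, 10% dropout, a two-sample t-test, 80% power and a smallest detectable effect of 0.78 SD. It frames this at day 28 and does not state alpha.

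- Evaluable patients: 30 × 0.9 = 27 per arm.
- Smallest detectable effect at 80% power with 27 per arm: 0.777 SD at two-sided 5%, 0.686 at 10%, 0.860 at 2.5%. The plan's 0.78 matches 5%, so two-sided 5% is assumed from here on.
- Power at 0.78 SD: 80.3%. The plan's figure reproduces.

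**3. Dilution.** Let *k* be the number of OCA patients using a sequestrant and *f* the share of the OCA effect each one loses. The documents give neither, so both are assumed. The average effect becomes

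d = 0.78 × (1 − (k/27) × f)

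| k | f | d (SD) | Power |
|---|---|---|---|
| 0 | – | 0.780 | 80.3% |
| 1 | 0.5 | 0.766 | 78.8% |
| 1 | 1 | 0.751 | 77.3% |
| 3 | 0.5 | 0.737 | 75.7% |
| 3 | 1 | 0.693 | 70.5% |

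One user costs 80.3 − 78.8 = 1.5 points at half loss and 80.3 − 77.3 = 3.0 points at total loss. Total loss means that the patient gets no OCA benefit over the whole treatment period, so it is an upper bound for one user. The rows for three users only show how the loss grows; nothing in the documents suggests that number.

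**The case against.** The strongest case on the other side is that no consequence has been shown.

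- **No documented use.** The documents report no sequestrant use in this population, and the binding statement is an expectation made for overdose, in a section that admits to having no specific information. It does not say how far ordinary use would lower exposure from 10 mg daily. This stands, and it keeps the point at the level of a cheap improvement.
- **Use would be seen.** All six contacts cover concomitant medication, and OCA and its conjugates are measured at Day 42. A low OCA value in such a patient would be a correct measurement and would help to reveal the problem. This also stands, but both controls find the loss after it has happened. Neither prevents it.
- **The error is in a known direction.** Dilution cannot create a false benefit. True, but a missed effect is still a cost in a trial with 30 patients per arm.
- **Other documents may carry a rule.** The Investigator's Brochure and the pharmacy procedures were not available. The gap is established for this protocol only.

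A reader might infer more than the documents support. The unused BAS abbreviation does not prove that a rule was dropped. Exclusion (d) shows that the sponsor wanted patients with impaired drug handling kept out, but its wording does not extend to medicines. C4, FGF19 and OCA levels are special investigations and not named endpoints, so an affected value does not compromise a stated objective.

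A reader might also look to the planned repeated-measures ANCOVA to absorb the loss, since section 10.2 says it will be more powerful than the t-test. No figure is put on that gain here. It depends on the baseline to follow-up correlation and on the two variances, which the documents do not give. The entry window of MELD above 11 and below 20 probably narrows the baseline spread, which makes an assumption of equal variances doubtful.

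**Conclusion.** The gap is real: the protocol expects a class of medicines to remove the study drug and sets no rule to keep the two apart during ordinary dosing. The likely harm is unknown and may be small. On the stated t-test, one OCA user costs 1.5 points of power at half loss and at most 3.0 points at total loss. Those figures rest on an assumed two-sided 5% level, 27 evaluable patients per arm, a true effect of 0.78 SD, and assumed values for the number of users and the share of effect lost.

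It would be wrong to conclude that the trial is underpowered or biased because of sequestrants, since no use is documented. The case for acting is that the loss, if it occurs, cannot be recovered in the analysis, while preventing it costs very little.

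**What to change.** Add to section 5.6:

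- Bile acid sequestrants should be avoided while the patient is taking study drug, except to treat an overdose. The restriction ends when study drug is stopped, including when it is stopped under section 4.3.1 for a rise in MELD or Discriminant Function, since those patients stay in the trial and may be offered any indicated treatment.
- If a sequestrant is clinically needed, separate it from the morning study dose by a fixed interval that the sponsor sets. Evening dosing is one example; the documents give no interval. Spacing gives only partial protection because of enterohepatic recirculation.

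Name sequestrants in the medication reviews already held at D0, D7, D14, D21, D28 and D42, and report use by arm. Leave the intention-to-treat analysis unchanged.

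Cost: a short addition to 5.6, one named item in six existing reviews, and one added summary line, because section 10 does not describe a concomitant-medication table. No extra visit or sample is needed. The downside is a minor limit on concomitant treatment during dosing.
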